Study Protocol and Statistical Analysis Plan

Study of Cerebral Structural and Functional Reorganization of Stroke Patients After Repetitive Transcranial Magnetic Stimulation (rTMS) Using the Method of Neuroimaging Brain Network Analysis

NCT Number: 03163758

Date:2013-1-1

[name]

Peking Union Medical College

[name]

Email: [contact]

Background: Many methods have been applied to facilitate recovery after stroke. However, improvement in rehabilitation strategies is necessary because many patients remain disabled after treatment^{1, 2}. Traditional methods, such as physical therapy and occupational therapy, are time-consuming and labor-intensive. Repetitive transcranial magnetic stimulation (rTMS) has been increasingly used for the treatment of depression, motor dysfunction after stroke, aphasia, and mental disorders since 2000^{3,91}. It is particularly popular in research studies on functional recovery and brain reorganization after stroke. Currently, the internationally recognized strategy is high-frequency (≥ 5 Hz) rTMS applied to the ipsilesional primary motor cortex (M1) to facilitate its reperfusion and reorganization¹⁰⁰. It has been proven to play a positive role in functional rehabilitation after stroke, and brain reorganization has been noted on functional magnetic resonance imaging (fMRI)^{9, 111}. However, low-frequency rTMS applied to the contralesional M1 may also facilitate recovery as it weakens the contralesional hemisphere's inhibitory effect on the ipsilesional hemisphere¹²¹. Some studies have used measurements, including clinical assessment, fMRI, motor evoked potentials (MEPs), and central excitatory time, to compare the two types of rTMS and have found no significant differences^{113, 141}. Many studies have demonstrated the positive role of rTMS in functional improvement, although these studies have varied in observation time and stages of stroke^{115, 161}. However, the onset and maintenance time of rTMS remain uncertain.

In this study, we aimed to evaluate the effectiveness of rTMS on motor rehabilitation after stroke using a longitudinal, prospective and randomized study, and to explore the central mechanism of rTMS in motor recovery after ischemic stroke through multimodal functional magnetic resonance imaging.

Methods:

Subjects

Patients aged 35-80 years, admitted to the Department of Peking Union Medical College Hospital between January 2013 and December 2018 for first onset of acute ischemic stroke will be included in this study. The study will be performed in accordance with the guidelines of the latest version of the Declaration of Helsinki. Subjects will be given written information and a verbal explanation concerning the study prior to obtaining consent for their participation.

Inclusion Criteria

The main inclusion criteria are: 1) stroke patients within 1 week after onset with unilateral cerebral subcortex lesion in the middle cerebral artery territory detected by diffusion weighted image (DWI), 2)

right-handed, 3) without memory loss or intelligence disorder, 4) never suffered stroke before.

Exclusion Criteria

The following patients will be excluded from the study: 1) direct damage to the cerebral cortex, a history of cerebral vessel disease, 2) tendency to hemorrhage or existed brain hemorrhage, 3) epilepsy or other mental disorders, 4) any MRI contraindications.

Grouping and Evaluation

The patients were divided into a real rTMS treatment group and a sham group randomly. A random number was generated by a computer, and the processing method was placed into a sealed envelope. A nurse who was not involved in the clinical evaluation was responsible for issuing and registering the number. The functional scores of the patients were independently assessed by an experienced neurologist at each follow-up time point. The staff members who implemented rTMS were not involved in the clinical assessment, and the rehabilitation physician was not aware of the patient groupings.

The scoring methods included the following: 1) National Institutes of Health Stroke Scale (NIHSS), 2) Barthel Index (BI), 3) Fugl-Meyer Assessment Upper Limb/Lower Limb (FMA-UL/LL), 4) modified Rankin Score (mRS), 5) the resting motor threshold (MT) of the hemiplegic upper limbs. The former 3 scores were the primary endpoints, and the latter 2 scores were the secondary endpoints. We evaluated each patient at 6 time points, including grouping time, the second day after treatment, 1 month after onset, 3 month after onset, 6 month after onset, and 1 year after onset.

rTMS

The MT (motor threshold) of the ipsilesional and contralesional abductor digiti minimi muscles were determined for every patient before rTMS or sham rTMS to evaluate motor function for both cerebral hemispheres. The RMT was defined as the lowest intensity capable of eliciting at least 5 MEPs of 50 μ V peak-to-peak amplitude in 10 consecutive stimulations when single-pulse TMS was delivered to the contralateral cortex. If the minimum MEP amplitude could not be detected, then it was recorded as 100%. MTs for bilateral cerebral hemisphere were recorded.

All patients received consecutive 10-day rTMS or sham rTMS. We used a Medtronic MagPro type magnetic stimulation device (Medtronic, Minneapolis, MN, USA) and a figure-eight coil (MC-B70, Medtronic). Regarding the safety threshold suggested by the International Federation of Clinical Neurophysiology (IFCN) and related studies, our protocol used 5 Hz rTMS applied to the ipsilesional M1. The treatment involved 50 trains of 20 pulses with 2-second intertrain intervals daily. In the rTMS

treatment group, coils were placed tangent to the scalp, while in the sham group, coils were placed perpendicular to the scalp.

Statistical analysis: Statistical analyses were performed using SPSS version 22.0 (IBM Corp., Armonk, NY, USA). Measurement data are described using means and standard deviations and were compared using the Mann-Whitney *U* test. Enumeration data were compared using the Chi-square test. A *P* value < 0.05 means significant difference.

References:

- [3] Ziemann U. Tms induced plasticity in human cortex. [J] *Reviews in the neurosciences*. 2004;15(4):253-266.

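### Does the lack of a written imaging endpoint, scan visit and imaging analysis, despite a title and aim about brain networks, require a change to the plan?

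*Combined protocol and SAP*

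**What the plan says.** The title describes the work as a study of structural and functional reorganisation "Using the Method of Neuroimaging Brain Network Analysis". The Background closes with two aims: to evaluate the effect of rTMS on motor rehabilitation, and "to explore the central mechanism of rTMS in motor recovery after ischemic stroke through multimodal functional magnetic resonance imaging".

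The Methods do not return to imaging as an outcome. Under Grouping and Evaluation, five measures are numbered: NIHSS, Barthel Index, Fugl-Meyer (upper and lower limb), modified Rankin score and resting motor threshold. Of these, "The former 3 scores were the primary endpoints, and the latter 2 scores were the secondary endpoints". The schedule reads "We evaluated each patient at 6 time points, including grouping time, the second day after treatment, 1 month after onset" and goes on to 3 months, 6 months and 1 year; no scan is attached to any visit. MRI appears in the Methods only in the eligibility criteria: diffusion-weighted imaging to identify the lesion, and exclusion of patients who cannot have MRI.

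The Statistical analysis paragraph names SPSS and says "Measurement data are described using means and standard deviations and were compared using the Mann-Whitney" U test, with the Chi-square test for counts. The threshold is that a P "value < 0.05 means significant difference". It mentions no covariate adjustment, multiplicity rule or imaging method.

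**The concern.** A study named after a brain-network analysis would be expected to say which network measure it uses, when patients are scanned and how the groups are compared. This plan says none of that. Clinical scores can show whether patients recover better, but not whether their brain networks reorganised. Motor threshold, recorded for both hemispheres, is a neurophysiological measure of the motor system and does not answer a network question either.

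Two consequences seem to follow. First, the second aim has no planned answer, so an imaging result could be chosen after the data are seen. Second, the only threshold in the document is an uncorrected 0.05. Carried over to network data, where tests can number in the thousands, it would produce many false positives, and a reader could not tell them from a mechanism.

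**Working it through.** **1. Is anything missing because of redaction or page removal?** The endpoint list, the visit list and the statistics paragraph each read as complete, with no blacked-out text. The omission belongs to the plan.

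**2. Is there a stated figure to reproduce?** No. The plan gives no sample size, power or number of imaging tests. Its only relevant figure is the 0.05 threshold, which is a convention and not a derived quantity.

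**3. What would happen if 0.05 were used on imaging data?** Every test count and correlation below is an assumption. Tests are taken as two-sided, with no true effect.

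For *m* tests, expected false positives = 0.05 × *m*. The chance of at least one is 1 − 0.95^*m* if the tests are independent. The values at correlation 0.5 and 0.8 come from simulating equally correlated normal statistics.

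| Summary measures | Expected | Chance of ≥1, independent | Correlation 0.5 | Correlation 0.8 |
|---|---|---|---|---|
| 5 | 0.25 | 0.23 | 0.18 | 0.13 |
| 10 | 0.5 | 0.40 | 0.29 | 0.17 |
| 20 | 1.0 | 0.64 | 0.42 | 0.22 |

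For connections between *k* regions, the number of tests is *k*(*k* − 1)/2:

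- 10 regions: 45 tests, 45 × 0.05 = 2.25 expected
- 20 regions: 190 tests, 190 × 0.05 = 9.5 expected
- 90 regions: 4,005 tests, 4,005 × 0.05 = 200.25 expected

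The mean does not depend on correlation, but the typical count does. With common correlation ρ, each statistic is √ρ·g + √(1 − ρ)·e, where g is shared. Given g, the chance that one test is significant is the normal tail beyond (1.960 − √ρ·|g|)/√(1 − ρ), plus the tail beyond (1.960 + √ρ·|g|)/√(1 − ρ). The median of |g| is 0.674 and its 95th percentile is 1.960.

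- ρ = 0.5, median: tails beyond 2.097 and 3.446, 0.0180 + 0.0003 = 0.0183; × 4,005 ≈ 73.
- ρ = 0.5, 95th percentile: tail beyond 0.812, 0.208; × 4,005 ≈ 835.
- ρ = 0.8, median: tail beyond 3.034, 0.0012; × 4,005 ≈ 5.
- ρ = 0.8, 95th percentile: tail beyond 0.463, 0.322; × 4,005 ≈ 1,290.

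With independent connections the median is about 200. The typical count thus ranges from about 5 to about 200 according to an unknown correlation, before the unknown number of tests is considered.

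**4. Does the plan apply 0.05 to imaging?** It does not say so. The statistics paragraph follows a Methods section whose only listed outcomes are the five scores and thresholds. Its wording, one test for measurements and one for counts, fits those outcomes. The arithmetic in step 3 shows what a poor analysis would do, not what this plan specifies.

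**5. What depends on the gap?** All three primary and both secondary endpoints are defined without imaging. Filling the gap or leaving it alters none of their comparisons.

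**The case for a change.** The strongest reply is that the argument in step 4 cuts both ways. If the 0.05 rule does not cover imaging, imaging has no rule at all, and the document presents itself as both protocol and SAP and refers to no separate imaging manual. An exploratory label does not remove the risk of selective reporting when the exploratory question is also the title. A short paragraph naming the scan visits, the measures, a baseline-adjusted comparison and a corrected threshold would cost little.

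The description of the gap stands, and such a paragraph would make the document better. It does not follow that the plan needs changing.

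- **No wrong rule is shown.** The complaint is that details are unwritten. Multiplicity correction and a choice of measures are what an imaging group would ordinarily supply.
- **The remedy rests on unknown facts.** The documents do not say that baseline and post-treatment research scans exist. If they do, adjusting for baseline would help: at an assumed baseline to follow-up correlation *r* of 0.5 to 0.7, the variance of a difference in means falls to 1 − *r*² = 0.75 to 0.51 of that from post-treatment values alone. Against change scores with equal variances the ratio is (1 + *r*)/2 = 0.75 to 0.85. If only the eligibility scan exists, there is nothing to adjust.
- **Prespecification may be out of reach.** Admissions run to December 2018, and much of the Methods is in the past tense. A measure named after the data have been seen would be post hoc however it was written.

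Whether the clinical scores themselves need adjustment or multiplicity control is a separate question and should not be decided through the imaging aim.

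**Conclusion.** The title and second aim promise more than the Methods specify: there is no imaging endpoint, no scan visit and no imaging analysis. This is missing detail on an exploratory aim, and no change to the plan follows. The effect on the primary and secondary clinical comparisons is nil. The false-positive risk for imaging is conditional on someone using uncorrected 0.05 for network data, which the plan does not say. Even then its size cannot be fixed: a chance of at least one false positive of 0.13 to 0.64 for 5 to 20 summary measures, and a median of about 5 to 200 false connections out of an assumed 4,005.

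The conclusion rests on two readings: that the statistics paragraph governs the listed scores, and that any imaging work will be corrected for multiplicity in the usual way and presented as exploratory. If an imaging report instead used uncorrected 0.05 or claimed to be confirmatory, that report should be criticised. Until then, imaging findings from this trial are hypothesis-generating.

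### Three primary scores at five post-baseline visits, with no primary visit and no rule for the effectiveness claim, leave that claim's error rate undefined: about 14–36% if any significant result counts

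*Combined protocol and SAP*

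**What the plan says.** The section on grouping and evaluation in the combined protocol and SAP lists five measures and then states: "The former 3 scores were the primary endpoints, and the latter 2 scores were the secondary endpoints". The first three are NIHSS, BI and "Fugl-Meyer Assessment Upper Limb/Lower Limb (FMA-UL/LL"). The section's own count is three primary scores. It does not say whether the upper- and lower-limb parts of FMA are summed or tested separately.

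On timing it says "We evaluated each patient at 6 time points". One is at grouping. The other five are "the second day after treatment, 1 month after onset, 3 month after onset, 6 month after onset, and 1 year after onset". None is called primary.

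The statistical analysis section is one short paragraph. "Measurement data are described using means and standard deviations and were compared using the Mann-Whitney" U test, and a P "value < 0.05 means significant difference". It gives no adjustment, no order of testing, and no statement of how many scores or visits must be significant.

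Two passages in the background bear on this. The aim is confirmatory in tone: "we aimed to evaluate the effectiveness of rTMS on motor rehabilitation after stroke". The text also notes that "the onset and maintenance time of rTMS remain uncertain", which is a reason to look at several visits.

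**The concern.** A randomised sham-controlled trial with a stated effectiveness aim needs a rule, fixed in advance, that says which result supports the claim. Here the only criterion is a threshold for a single comparison, and there are at least 15 comparisons to which it could apply (3 scores × 5 visits).

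Without a rule, the scale and the visit that carry the claim can be chosen after the results are seen. The stated 0.05 is then not the error rate of the claim. How far off it is depends on a choice that the plan leaves unwritten.

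**Working it through.** **No plan figure to reproduce.** The documents give no sample size, power or overall error rate.

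**Inputs from the documents.** Primary scores: 3 (4 only if FMA-UL and FMA-LL are tested separately). Post-baseline visits: 6 − 1 = 5. Threshold: 0.05 per comparison. Tests: 3 × 5 = 15, or 4 × 5 = 20.

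**Assumptions.** Tests are two-sided (critical value 1.96). Test statistics are approximately normal. Pairwise correlation ρ is 0.5 to 0.9. The documents give no correlations, so results are shown across that range.

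**1. Any significant result counts, no true effect.** With a common correlation ρ and k tests:

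P(at least one) = 1 − ∫ φ(u) [Φ((1.96 − √ρ·u)/√(1−ρ)) − Φ((−1.96 − √ρ·u)/√(1−ρ))]^k du

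Dropping the second Φ term gives the chance of a difference favouring rTMS.

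| Tests | Direction | ρ = 0.9 | ρ = 0.7 | ρ = 0.5 |
|---|---|---|---|---|
| 15 (3 scores × 5 visits) | either | 14.4% | 25.6% | 36.1% |
| 15 | favouring rTMS | 7.2% | 12.8% | 18.1% |
| 20 (4 scores × 5 visits) | either | 15.5% | 28.9% | 41.9% |
| 20 | favouring rTMS | 7.8% | 14.5% | 21.0% |
| 3 (3 scores, one visit) | either | 8.4% | 10.9% | 12.5% |
| 5 (one score, 5 visits) | either | 10.2% | 14.8% | 18.3% |

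The nominal figures for a single test are 5% in either direction and 2.5% favouring rTMS. If the correlation between visits decays with distance (AR(1), adjacent visits at 0.5), one score over five visits gives about 20%.

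**2. Sensitivity to structure.** With score correlation 0.5 and AR(1) visits at 0.5, simulation gives about 44% (three scores) and 52% (four). In the four-score case 76% of the 190 pairs correlate below 0.5, with mean 0.24, so these are not results for correlations of 0.5–0.9.

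**3. Sensitivity to sample size.** Simulated Mann-Whitney tests with 15, 30 and 60 patients per arm (assumed sizes), three scores, gave 14.5%, 14.4% and 15.3% at common ρ = 0.9. They gave 42.9%, 44.0% and 43.8% under the AR(1) structure at 0.5. The unstated sample size matters little.

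**4. All scores required at one fixed visit, favouring rTMS.**

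P(all) = ∫ φ(u) [Φ((√ρ·u − 1.96)/√(1−ρ))]^k du

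For ρ = 0.5, 0.7, 0.9 this is 0.16%, 0.44%, 1.13% (three scores) and 0.07%, 0.29%, 0.94% (four), when no score has an effect. If one score has no effect and each of the others has 80% power, it is 2.4–2.5%. It cannot exceed 2.5%, because the null score must itself be significant.

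If the visit is left open, so that any of the five may count, that last case rises to about 5–10%. An all-scores rule therefore also needs a fixed visit.

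**5. Power under the remedies.** 80% power at two-sided 0.05 corresponds to a shift of 1.960 + 0.842 = 2.802.

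- *Holm, only one score has an effect.* First-step levels are 0.05/3 = 0.0167 (critical value 2.394) and 0.05/4 = 0.0125 (2.498). Power is Φ(2.802 − 2.394) = 66% and Φ(2.802 − 2.498) = 62%.
- *Holm, 80% power on every score.* The chance of at least one significant score at ρ = 0.5, 0.7, 0.9 is 87%, 83%, 76% (three) and 88%, 83%, 74% (four).
- *All scores required, 80% power on each.* Joint power at ρ = 0.5 to 0.9 is 61–72% (three) and 56–70% (four).

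**The case against.** The correlations are assumed, and the plan never says that any one significant result would count. Both points are fair, and they limit what can be said. A reader might make three stronger inferences that the documents do not support.

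- *That the false-positive chance is as high as 52% for correlations of 0.5–0.9.* That figure needs four scores and a structure in which most pairs correlate well below 0.5. The plan counts three scores, and a common correlation in that range gives 14–36%.
- *That the right contrast is 14–36% against about 1%.* The first counts differences in either direction. The second counts only those favouring rTMS, and only when no score has an effect. Like for like with three scores, it is 7–18% against 0.2–1.1%, or up to about 2.5% when one score has no effect.
- *That the text adopts an any-result rule, or supports an any-result and an all-scores reading equally.* It states only a threshold per comparison. Both rules are constructions used here to show how much depends on the choice.

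It can also be said that repeated visits suit the question of onset and maintenance. They do, and they can all stay in the report. Only the effectiveness claim needs a single rule.

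None of this supplies the missing rule. Even at a correlation of 0.9, three scores at one visit exceed 5% if any result counts.

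**Conclusion.** The gap is real and should be closed before the effectiveness claim is tested. The plan names three primary scores and five post-baseline visits, and no primary visit, multiplicity procedure or decision rule.

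The overall error could lie well above or well below the nominal level, depending on a rule that is not written. The any-result figures rest on assumed common correlations of 0.5–0.9, two-sided tests and no true effect. They rise to about 16–42% if FMA is split into two scores, and to about 44% (three scores) or 52% (four) if distant visits correlate below 0.5. That the unwritten rule determines the error rate holds under every structure examined. The exact percentages do not.

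**What to change.** Before outcomes are examined by group, add one paragraph to the SAP that does the following.

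1. States how FMA-UL and FMA-LL are combined, or that they are separate scores.
2. Names one primary score at one visit of the sponsor's choosing, for example total FMA, which matches the motor aim. The deciding test is the planned Mann-Whitney U at two-sided 0.05.
3. Makes the other scores and visits secondary, or tests the scores at the primary visit in a written order, each at 0.05, stopping at the first non-significant result.
4. Reports the other four visits as group differences with 95% confidence intervals (for example Hodges-Lehmann, which pairs with Mann-Whitney), stated not to decide the claim.

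If all the primary scores are kept, fix one visit and choose either Holm or a rule that every score must be significant in favour of rTMS, each at 0.05.

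**Cost.** No new data. With a single primary, that comparison loses no power, but NIHSS and BI can no longer carry the claim alone. With three scores under Holm, a score that is the only one with an effect goes from 80% to about 66% power; if every score has 80% power, the chance of at least one significant score is about 76–87%. Requiring all three gives joint power of about 61–72%. The four-score figures are in the working.

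The methods text is partly in the past tense, so whether outcomes have already been examined by group is open. If they have, a rule written now cannot restore the stated error rate, and the results should be labelled exploratory.

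### Lesion-side MEP status is recorded before treatment but not used in the comparison of arms; if it is prognostic, the unadjusted test gives up power that a prespecified stratum would recover

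*Combined protocol and SAP*

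**What the plan says.** In the section headed rTMS, motor thresholds of the hand muscle on both sides "were determined for every patient before rTMS or sham rTMS to evaluate motor function for both cerebral hemispheres". A threshold requires at least 5 responses of 50 μV in 10 consecutive stimulations. The plan foresees patients who have none: "If the minimum MEP amplitude could not be detected, then it was recorded as 100" per cent. Such patients stay in the trial. The Inclusion Criteria ask for "stroke patients within 1 week after onset with unilateral cerebral subcortex lesion in the middle cerebral artery territory" and the Exclusion Criteria end with "epilepsy or other mental disorders, 4) any MRI contraindications"; neither list mentions the MEP.

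Under Grouping and Evaluation, allocation is described as "A random number was generated by a computer, and the processing method was placed into a sealed envelope". No strata, blocks or minimisation are mentioned. NIHSS, BI and FMA (upper and lower limb) are the primary endpoints; mRS and resting motor threshold are secondary. All five are listed for every assessment, including the one at grouping.

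Under Statistical analysis, "Measurement data are described using means and standard deviations and were compared using the Mann-Whitney" U test, with a Chi-square test for counts. No covariate, stratum, subgroup or change-from-baseline analysis is given.

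**The concern.** MEP status is a yes/no baseline factor that the trial collects in everyone, for the declared purpose of judging motor function. The primary endpoints are motor and functional scores, and stimulation is applied to the ipsilesional motor cortex, whose output the lesion-side MEP tests. It is therefore reasonable to suspect that patients with and without an MEP differ in their later scores.

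If they do, two things follow for an unadjusted test. Differences between the MEP groups add to the spread within each arm, so a real effect is harder to detect. And if one arm happens to receive more MEP-absent patients, the observed difference moves with that imbalance and nothing in the analysis corrects it. What is at stake is precision in a trial whose aim is to evaluate effectiveness on motor rehabilitation.

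**Working it through.** **Inputs.** The plan states no sample size, power, effect size, SD or MEP-absent share, so there is no figure of its own to reproduce. From the plan: two arms, Mann-Whitney test, P < 0.05. Assumed: 1:1 allocation, two-sided test, MEP-absent share q of 20-40% (up to 50% where stated), 20 or 40 patients per arm.

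**1. Chance imbalance.** With n per arm, the SD of the difference between arms in MEP-absent share is √(2q(1−q)/n).
- n = 20: √(0.32/20) = 12.6 points at q = 0.2; √(0.48/20) = 15.5 points at q = 0.4.
- n = 40: √(0.32/40) = 8.9 points; √(0.48/40) = 11.0 points.

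From exact binomial counts with q = 0.2-0.5, the chance that the arms differ by 20 points or more is 16-27% at 20 per arm, 8-16% at 30, 2-6% at 50 and at most 1% at 100. A 20-point imbalance moves the crude difference in mean score by 0.20 × gap: 0.20 × 10 = 2 FMA-UL points, 0.20 × 15 = 3, or 0.20 × 30 = 6.

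**2. Added variance.** If the MEP groups differ by D within-group SDs, the total variance is the within-group variance × [1 + q(1−q)D²]. At D = 1 the factor is 1.16 (q = 0.2) to 1.25 (q = 0.5). Take a trial of 63 per arm, with 80% power for a 0.5 SD effect when MEP status is accounted for. Ignoring MEP status, power is 78-79% at D = 0.5, about 71-74% at D = 1 and 51-59% at D = 2. The number per arm needed for 80% rises from 63 to 73-79 at D = 1 and to 103-126 at D = 2.

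**3. Gain from stratifying the analysis only.** Simulated FMA-UL on its 0-66 range: MEP-present mean 50, SD 10; MEP-absent mean lower by the gap, SD 12; treatment shift 7; simple randomisation throughout. The planned Mann-Whitney test is set against the van Elteren test, its stratified form.

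| Assumed gap (FMA-UL points) | Gain in power (percentage points), 20-40 per arm |
|---|---|
| 0-5 | about 0-2 |
| 10 | 4-6 |
| 15 | 8-15 |
| 30 | 20-42 |

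For gaps of 15-30 points, power is 20-43% pooled against 45-51% stratified at 20 per arm, and 37-74% against 79-83% at 40 per arm. In SD units (mean SD about 11) these gaps are 15/11 ≈ 1.4 and 30/11 ≈ 2.7, so the lower rows of the table describe large to extreme separation.

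**4. False-positive rate.** In null simulations (2,000 per setting; D = 0, 1 or 2; 25 or 63 per arm) the unadjusted test rejected in 3.5-6.2% of trials. The highest value came at D = 0, where there is no gap between MEP groups, so it is not caused by mixing them.

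**5. Cost if MEP status is not prognostic.** At D = 0, the stratified test had 74-76% power against 76-77% at 25 per arm, and 77% against 77-78% at 63 per arm: a loss of under 2 points.

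**The case against.** The documents nowhere say that MEP-absent patients recover differently, respond differently or are numerous. They say only that the threshold is taken "to evaluate motor function for both cerebral hemispheres". This stands, and it is why the size can only be conditional. Failing a 5-in-10 criterion in one hand muscle also does not prove absence of motor output, and a hand muscle is a weak guide to FMA lower limb, BI or NIHSS.

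Much of the benefit may also come from the baseline score instead. In simulated change from baseline, with the same MEP gap at both times and an assumed within-group correlation of 0.6, power at 15-30 point gaps was 54-56% unstratified and 52-56% stratified at 20 per arm, and 84-86% for both at 40. MEP status then adds nothing unless it predicts recovery beyond the baseline score. This stands too, though the plan specifies no baseline adjustment either.

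A reader might infer three stronger points, which the documents do not support:
- **The result is biased.** Randomisation protects the test on average, and step 4 of the working shows no systematic inflation. The harm is lost precision and possible chance imbalance in the one trial that is run.
- **Randomisation must be stratified.** All that is said of allocation is "The patients were divided into a real rTMS treatment group and a sham group randomly" and that a computer-generated number and envelopes were used. Stratifying both allocation and analysis gives 48-53% power at 20 per arm and 79-84% at 40, close to the 45-51% and 79-83% from stratifying the analysis alone.
- **The pooled result hides an effect confined to MEP-present patients.** Nothing in the plan shows this, and a subgroup report could hardly test it: at 20 per arm and a 20% share there are 40 × 0.2 = 8 MEP-absent patients, about 4 in each arm.

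**Conclusion.** The point holds as a missed, nearly free gain in precision. The plan collects a plausible prognostic factor in every patient and leaves it out of the comparison. Under the stated assumptions the gain in FMA-UL power runs from nothing (gap of 5 points or less), through a modest 4-6 points (gap of 10), to a substantial 8-15 points (gap of 15); the 20-42 points at a 30-point gap is an extreme case. The effect of the gap on BI, NIHSS and FMA lower limb was not quantified. The risk of a marked imbalance matters mainly at about 30 patients or fewer per arm. It would go too far to say that the trial mixes two known recovery courses: the plan makes a difference plausible and gives no evidence for one.

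**What to change.** Add to Statistical analysis: the primary comparisons are stratified by baseline lesion-side MEP status (present or absent by the criterion in the rTMS section), using the van Elteren test, or a rank-based model with MEP status and the baseline score. The second option is preferable if the baseline score is to be used at all. Report MEP status by arm in the baseline table. Label any result by MEP stratum as descriptive.

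Record presence or absence as its own yes/no item, before the envelope is opened, so that the stratum cannot depend on the allocation. Separate envelope series are optional. For patients already randomised, the analysis stratum alone is enough, provided their pre-treatment MEP status was recorded.

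Cost: one more analysis step and no new measurement. The loss of power is negligible if MEP status turns out not to be prognostic.
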